## **2. STUDY OBJECTIVES AND HYPOTHESES**

### **2.1. Study Objectives**

#### **2.1.1. Primary Objectives**

##### **2.1.1.1. Part 1 (Dose Escalation)**

The primary objectives of Part 1 are as follows:

1. To assess the safety and tolerability of DS-3201b in subjects with relapsed/refractory AML or ALL.
2. To determine the MTD and RDE of DS-3201b in subjects with relapsed/refractory AML or ALL.

##### **2.1.1.2. Part 2 (Dose Expansion)**

The primary objective of Part 2 is as follows:

1. To confirm the safety and tolerability of DS-3201b at the RDE in subjects with relapsed/refractory AML and ALL.

#### **2.1.2. Secondary Objectives**

##### **2.1.2.1. Part 1 (Dose Escalation)**

The secondary objective of Part 1 is as follows:

1. To assess the plasma PK after single and multiple doses of DS-3201b.

##### **2.1.2.2. Part 2 (Dose Expansion)**

The secondary objectives of Part 2 are as follows:

1. To assess overall response rate (ORR) in subjects with relapsed/refractory AML and ALL using the revised International Working Group (IWG) response criteria and NCCN response criteria, respectively, duration of response (DOR), and OS.
2. To assess the PK after single and multiple doses of DS-3201b.

#### **2.1.3. Exploratory Objectives**

##### **2.1.3.1. Part 1 (Dose Escalation)**

The exploratory objectives of Part 1 are as follows:

1. To assess the PDy of DS-3201b, such as trimethylation status of H3K27 and quantitation of leukemic stem cells, in pre- and post-dose blood and/or bone marrow samples.
2. To evaluate response to DS-3201b per revised IWG response criteria in subjects with relapsed/refractory AML or NCCN response criteria in subjects with relapsed/refractory ALL.

### **2.1.3.2. Part 2 (Dose Expansion)**

The exploratory objectives of Part 2 are as follows:

1. To evaluate the relationship between response rate in relapsed/refractory AML and ALL and cytogenetic and molecular-based biomarkers studied in pre-treatment bone marrow biopsies and/or blood samples.
2. To assess the PDy of DS-3201b.
3. To compare CR duration between that observed with DS-3201b treatment and that observed from the most recent therapeutic regimen.

## **2.2. Study Hypothesis**

DS-3201b will be well-tolerated and will exhibit acceptable PK/PDy response properties in subjects with relapsed or refractory AML or ALL. DS-3201b will manifest activity as evidenced by objective response in subjects with relapsed or refractory AML or ALL, using the appropriate response criteria according to the revised IWG guidelines (for AML) or NCCN guidelines (for ALL).

### 3. STUDY DESIGN

[figure not shown]
#### 3.1. Overall Plan

##### 3.1.1. Study Type

This will be a Phase 1, non-randomized, open-label study of DS-3201b in subjects with relapsed/refractory AML or ALL. This 2-part study will include both a Dose Escalation portion to assess the safety and tolerability of DS-3201b, identify a RDE, assess its PK/PDY properties, and evaluate the response to DS-3201b by revised IWG or NCCN response criteria for AML and ALL, respectively, and a Dose Expansion portion to confirm the safety and tolerability of DS-3201b at the RDE, assess the ORR, DOR, and OS, evaluate the relationship between response rate and selected cytogenetic and molecular biomarkers studied in pre-treatment bone marrow biopsies and/or blood samples, assess the PK and PDY of DS-3201b, and compare CR duration between that observed with DS-3201b treatment and that observed from the most recent therapeutic regimen.

Up to 10 sites in the United States are planned for the study. A schematic diagram of the study is provided in Figure 3.1.

**Figure 3.1: Study Flow Chart**

Note: In Dose Escalation, cohorts may be expanded below the MTD dose level (at any time following conclusion of that cohort's safety window) or at the MTD in parallel with ongoing escalation up to a maximum of 20 subjects in each cohort for further elaboration of safety, PK, or PDY response parameters as deemed appropriate by Investigators and Sponsor in order to define the RDE.

### 3.1.2. Treatment Groups

In this Phase 1, non-randomized, open-label study, each subject will be administered DS-3201b orally once daily over a 28-day cycle (1 cycle). In the first cohort, study treatment initiation will be staggered. A delay of at least 7 days will occur between the first subject dosed and the second and third subjects dosed. In subsequent cohorts, the study treatment can be started in the second and third subjects 1 day after first administration in the first subject.

The starting dose will be 100 mg/day as a single dose. The dose will be administered without food (no food for at least 2 hours before and 1 hour after the dose). A missed dose of DS-3201b may be administered later that same day (until midnight). The dose will be assessed as a missed dose if not administered. No replacement dose is administered if the subject vomits after taking DS-3201b.

After discontinuation of the study treatment, subjects will be contacted for an End-of-study (EOS) Follow-up visit 30 ( $\pm$  5) days after the last dose of study drug, followed by a Long-term Follow-up (LTFU) period with follow-up contact every 3 months via telephone until death, loss to follow-up, or termination of study by the Sponsor (see Section 6.4).

#### 3.1.2.1. Part 1 (Dose Escalation)

Dose escalation of DS-3201b to determine the MTD will be guided by a Bayesian logistic regression model (BLRM), following the escalation with overdose control (EWOC) principle. The logistic regression model for the DLT rate will include 2 parameters: the intercept and the slope. After the first 3 subjects of each cohort complete the DLT evaluation during Cycle 1 (see Section 3.1.7.2), the posterior distributions of the DLT rate will be derived for all provisional dose levels based on the BLRM using the DLT outcome data from all assessed doses and a pre-specified prior distribution for the model parameters. The posterior probability of the DLT rate in the following 4 intervals at each dose level ([0%, 16%) as the DLT rate interval for under-dosing, [16%, 33%) as the target DLT rate interval, [33%, 60%) as the DLT rate interval for excessive toxicity, and [60%, 100%) as the DLT rate interval for unacceptable toxicity) will then be calculated and used for dose recommendation for the next cohort according to the EWOC principle.

The EWOC principle requires that the BLRM recommended dose for the next cohort of subjects is defined as the highest posterior probability of the DLT rate in the target DLT rate interval [16%, 33%) among all dose levels fulfilling the overdose control constraint: there is less than a 25% probability for the DLT rate  $>33\%$  (probability for excessive or unacceptable toxicity). The dose increment will be as follows:

- The dose level increment should be no less than 30% in order to have distinction among dose levels considering the inter-subject variability in exposure, but flexibility may be applied in selecting the dose to accommodate the available dosage form strengths.
- The dose level increment should be no more than 100% even if the model suggests a higher dose than 100% for the next cohort.

Cohorts of 3 to 6 subjects will be enrolled and assessed for DLT before escalation to a new higher dose. In the event of a DLT, the next 2 subjects will receive DS-3201b treatment starting

at least 1 week apart. As an exception, the model will be reevaluated before enrollment of any additional subjects to the cohort if 2 evaluable subjects experience DLT before the enrollment of the next subject after the BLRM dose recommendation. The dose for the next cohort will be chosen by the Sponsor and Principal Investigators based on the dose recommendation by the BLRM, clinical assessment of toxicity profiles and efficacy, and PK/PDy information observed thus far.

Based on the safety results available so far from the Phase 1 study of DS-3201 currently ongoing in Japan (DS3201-A-J101), escalation from the starting dose of 100 mg to the second dose level will be by less than 100%.

Enrollment of subjects to a new cohort requires completion of a DLT evaluation of at least 3 subjects treated in the current cohort. Subjects who have neither completed a DLT evaluation nor experienced a DLT will not be included in the BLRM update. In the event that subjects in the previous cohort experience a DLT after the enrollment of subjects to a new cohort has begun, dose level assignment of the next subject in the new cohort will be based on an updated BLRM using DLT outcome data from all assessed doses.

For a subject to be considered evaluable for dose escalation decisions, the subject must have received at least 75% of the doses (ie, 21 days) during the DLT evaluation period or experienced a DLT in Cycle 1. The final MTD will be decided based on considerations of the respective MTD estimated by the BLRM, and on an overall assessment of safety data from subsequent cycles and of PK/PDy response collected at all different doses tested. For dose determination, the following stopping rules will be implemented for the Dose Escalation part: (a) at least 6 evaluable subjects at the MTD level with at least 21 evaluable subjects in total enrolled in the Dose Escalation part, (b) at least 9 evaluable subjects have been enrolled at a dose level which is the model's recommendation for the next dose cohort and for which the posterior probability of targeted toxicity is at least 50%, or (c) dose level 1 is too toxic.

Cohorts may be expanded below the MTD dose level (at any time following conclusion of that cohort's safety window) or at the MTD in parallel with ongoing escalation up to a maximum of 20 subjects in each cohort for further elaboration of safety, PK, or PDy response parameters as deemed appropriate by Investigators and Sponsor in order to define the RDE. Further details can be found in the Cohort Management Plan.

### **Dose escalation using alternative drug administration schedule**

Based on safety, PK data, and PDy data collected during Dose Escalation using the QD × 28/28 days schedule of DS-3201b, alternative, less frequent drug administration schedules for dose escalation may be considered following review by the Principal Investigators and Sponsor. Modeling and simulation will be performed to evaluate DS-3201 exposure relationship to PDy and toxicity. If the results indicate that using an alternative dosing schedule may provide less toxicity (eg, myelosuppression) while offering pharmacodynamic benefits based on available biomarkers or a better PK profile, dose escalation using this recommended alternative dosing schedule will be performed in lieu of, or in parallel with, the QD × 28/28 days schedule. For example:

If the recommended dosing schedule is less frequent than QD × 28/28 days (eg, QD × 14/28 days, or QD × 7/28), the starting daily dose of the new schedule will be same as the

highest daily dose tested for the QD × 28/28 day schedule that showed DLT in less than one-third of evaluable subjects.

Dose escalation/de-escalation in the alternative schedule will follow the BLRM method as described in Section 11.11 in order to determine an MTD for the alternate dose schedule. When both the original QD × 28/28 days and alternative dosing schedules are explored in parallel, limiting a site to only 1 active regimen may be done at the discretion of the Sponsor. The final MTD for each dosing schedule will be decided based on considerations of the respective MTDs estimated by the BLRM, and on an overall assessment of safety data from subsequent cycles and PK/PDy information collected at all different doses tested. Upon determining the final MTD of the original QD × 28/28 days and/or alternative dosing schedules, 1 dosing regimen will be selected for further evaluation in Part 2 (Dose Expansion). This regimen given at the final MTD determined in Part 1 is referred to as the “recommended dose for the expansion phase”.

### **3.1.2.2. Part 2 (Dose Expansion)**

Upon completion of Part 1 with the established MTD, RDE, and drug administration schedule, the Dose Expansion part will begin with the intention of confirming the safety and tolerability of DS-3201b and evaluating preliminary efficacy of DS-3201b in 2 separate cohorts of subjects with relapsed or refractory AML and ALL.

Four subjects with AML and 4 subjects with ALL will initially be treated to further assess safety before enrolling the remaining subjects in the respective cohorts of AML and ALL. Following completion of the Cycle 1 safety evaluation in all 4 subjects in the cohort, a safety analysis will be conducted to allow the reevaluation of the appropriateness of the dosing level. If the incidence of DLT has exceeded the EWOC principle guideline, no further treatment at the MTD and RDE level established in Part 1 will be done and dose de-escalation will be considered. Approximately 20 subjects each with AML and ALL will be enrolled in Part 2 to obtain a sufficient number of subjects treated at the RDE in these indications.

Pre-treatment bone marrow biopsies/aspirates will be required for participation in the study and optional post-treatment bone marrow biopsies/aspirates may be collected within 30 days following the last dose of study drug treatment.

### **3.1.2.3. Intrasubject Dose Escalation**

No intrasubject dose escalation will be permitted.

## **3.1.3. Study Endpoints**

The endpoints for the study include the following:

- Pharmacokinetic Parameters**

Cycle 1/Days 1 and 2 (Part 1 and Part 2):

- Maximum (peak) plasma concentration (Cmax), time to reach maximum plasma concentration (Tmax), area under the plasma concentration-time curve up to the last quantifiable time (AUClast)
- If appropriate: Area under the plasma concentration-time curve up to infinity (AUCinf), terminal elimination half-life (t1/2), apparent total body clearance

following a single dose administration (Cycle 1/Day 1) (CL/F), apparent volume of distribution based on the terminal phase (Vz/F)

Cycle 1/Day 8 (Part 1 and Part 2):

- Cmax, Tmax, AUClast, and comparison of Cmax and AUClast values between Day 8 and Day 1 (Cmax and AUClast ratio) (d8,d1)
- If appropriate: Area under the plasma concentration-time curve during dosing interval (AUCtau), AUCinf, t1/2, apparent total body clearance at steady state following multiple dose administration (Cycle 1/Day 8) (CLss/F), apparent volume of distribution at steady state after multiple-dose administration (Vss/F)

Cycle 1/Days 2, 8, 15, and 22 and Cycle 2/Day 1 (Part 1 and Part 2):

- Trough plasma concentration (Ctrough)

End-of-treatment (EOT) (Part 1 and Part 2):

- Ctrough

- **Exploratory Biomarker Parameters**

- Exploratory molecular testing in blood cells and/or bone marrow cells (at pre-dose and post-dose time points)
- Retrospective confirmatory analysis and correlation with pre-therapy cytogenetic and molecular subsets of AML or ALL to response

- **Pharmacodynamic Parameters**

- Quantitation of leukemic stem cells in pre- and post-dose bone marrow cells by flow cytometry and/or mass cytometry
- H3K27me3 status in leukemic stem cells in bone marrow and/or blood cells

- **Efficacy Parameters**

Primary efficacy variable is response to treatment, which will be defined per the revised IWG response criteria for AML or standard response criteria for ALL as defined in Appendix Section 17.3 (NCCN 2016 ALL response criteria).

The efficacy endpoints will be:

- Composite complete remission (CRc) rate, including complete remission (CR), complete remission with incomplete blood count recovery (CRI), and CRp
- Morphologic leukemia-free state (MLFS)
- Partial remission (PR) rate
- Overall response rate (ORR) = CRc+PR
- Duration of response (DOR): Time from the first objective evidence of response to the first objective evidence of disease progression
- Overall survival (OS): Time from the date of enrollment to the date of death from any cause
- 30- and 60-day mortality rate

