## LIST OF ABBREVIATIONS

ABBREVIATION	DEFINITION
AAG	Alpha 1-acid glycoprotein;
AE	Adverse event
ALL	Acute lymphocytic leukemia
ALT	Alanine aminotransferase
AML	Acute myelogenous leukemia
ANC	Absolute neutrophil count
aPTT	Activated partial thromboplastin time
ASR	Age standardized rate
AST	Aspartate aminotransferase
ATL/L	Adult T-cell leukemia-lymphoma
AUC	Area under the plasma concentration-time curve
AUC inf	Area under the plasma concentration-time curve up to infinity
AUClast	Area under the plasma concentration-time curve up to the last quantifiable time
AUClast ratio	Comparison of AUClast values between Day 8 and Day 1
AUC tau	Area under the plasma concentration-time curve during dosing interval
BLRM	Bayesian logistic regression model
C max	Maximum plasma concentration
C max ratio	Comparison of C max values between Day 8 and Day 1
C trough	Trough plasma concentration
CFR	Code of Federal Regulations
CL/F	Apparent total body clearance
CL ss /F	Apparent total body clearance at steady state
CNS	Central nervous system
CR	Complete remission
CRc	Composite complete remission
CRi	Complete remission with incomplete blood count recovery
CRp	Complete remission with incomplete platelet recovery
CRF	Case report form
CRO	Contract research organization
CSPV	Clinical Safety and Pharmacovigilance

ABBREVIATION	DEFINITION
CTCAE	Common Terminology Criteria for Adverse Events
CYP	Cytochrome P450
DLT	Dose-limiting toxicity
DNA	Deoxyribonucleic acid
DOR	Duration of response
DRF	Dose range finding
DS-3201a	The free form of DS-3201b
DSI	Daiichi Sankyo, Inc.
ECG	Electrocardiogram
ECOG	Eastern Cooperative Oncology Group
eCRF	Electronic case report form
EDC	Electronic data capture
EIU	Exposure in utero
EOS	End-of-study
EOT	End-of-treatment
EWOC	Escalation with overdose control
EZH	Enhancer of zeste homolog
FOB	Functional observational battery
F/U	Follow-up
GCP	Good Clinical Practice
GI 50	Concentrations causing 50% growth inhibition
GLP	Good Laboratory Practice
GVHD	Graft-versus-host disease
H3K27	Lysine 27 in histone H3
H3K27me3	H3K27 trimethylation
hERG	Human ether- à -go-go related gene
HNSTD	Highest non-severely toxic dose
HCT	Hematopoietic cell transplantation
IC 50	Half maximal inhibitory concentration
ICF	Informed consent form
ICH	International Council for Harmonisation
INR	International normalized ratio

ABBREVIATION	DEFINITION
IRB	Institutional Review Board

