In rats and dogs, exposures from daily dose administration up to 4 weeks in duration generally demonstrated dose-proportionality across a range of doses from sub-efficacious to above the maximum tolerated dose (MTD). There was no consistent evidence of accumulation after repeated dosing and there were no differences in exposure between males and females.  $T_{1/2}$  was from 2.29 hours to 7.14 hours in rats and from 1.73 hours to 5.88 hours in dogs.  $T_{max}$  on Day 28 ranged from 0.5 hours to 1.3 hours in dogs and from 1 hour to 24 hours in rats.

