### **6.3.1.2. Part 1 (Dose Escalation), Cycle 1/Day 2**

The following procedures will be performed pre-dose during the Part 1, Cycle 1/Day 2 visit.

- Obtain vital sign measurements (systolic and diastolic blood pressure, pulse rate, respiratory rate, and body temperature).
- Obtain blood samples for clinical laboratories (Section [9.7](#)).
- Obtain a blood sample for DS-3201a PK measurement.
- Obtain a blood sample for protein binding determination.
- Obtain a blood sample for histamine measurement.
- Obtain a blood sample for biomarkers.
- Perform a 12-lead ECG in triplicate (5 minutes apart).
- Record concomitant medications.
- Assess subjects for AEs.
- Administer DS-3201b per protocol (at the site).
- Dispense DS-3201b per protocol (to take home).
- Dispense a pill diary with dose administration instructions to assess treatment compliance.

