### **6.3.1.3. Part 1 (Dose Escalation), Cycle 1/Day 8**

The following procedures will be performed pre-dose during the Part 1, Cycle 1/Day 8 visit ( $\pm 2$  days):

- Perform a complete physical examination and record weight.
- Obtain vital sign measurements (systolic and diastolic blood pressure, pulse rate, respiratory rate, and body temperature).
- Assess functional status using the ECOG-PS Scale (Section [17.1](#)).
- Obtain blood samples for clinical laboratories (Section [9.7](#)).
- Obtain a blood sample for DS-3201a PK measurement.
- Obtain a blood sample for protein binding determination.
- Obtain a blood sample for histamine measurement.
- Obtain a blood sample for biomarkers.
- Obtain serum for AAG measurements.

- Obtain a urine sample for urinalysis (Section 9.7).
- Perform a 12-lead ECG in triplicate (5 minutes apart).
- Record concomitant medications.
- Assess subjects for AEs.
- Obtain bone marrow biopsies/aspirates for marrow assessment and/or biomarker tests.
- Administer DS-3201b per protocol (at the site).
- Dispense DS-3201b per protocol (to take home), if needed.
- Dispense and review pill diary to assess treatment compliance.
- Review of returned study medication and assessment of compliance.

The following procedures will be completed post-dose during the Part 1, Cycle 1/Day 8 visit:

- Perform a 12-lead ECG in triplicate at 1, 2, 4, and 8 hours post-dose (5 minutes apart).
  - Note: If the ECG at 8 hours post-dose is not possible, then ECG may be performed at 6 hours ( $\pm$  10 minutes) post-dose.
- Obtain blood samples for DS-3201a PK measurements and for protein binding determination at the following time points: 0.5, 1, 2, 4, 6, and 8 hours post-dose.

#### 6.3.1.4. Part 1 (Dose Escalation), Cycle 1/Day 15

The following procedures will be completed pre-dose during the Part 1, Cycle 1/Day 15 visit ( $\pm$  2 days):

- Perform a complete physical examination and record weight.
- Obtain vital sign measurements (systolic and diastolic blood pressure, pulse rate, respiratory rate, and body temperature).
- Assess functional status using the ECOG-PS Scale (Section 17.1).
- Obtain blood samples for clinical laboratories (Section 9.7).
- Obtain a blood sample for DS-3201a PK measurement.
- Obtain a blood sample for histamine measurement.
- Obtain a blood sample for biomarkers.
- Obtain a blood sample for protein binding determination.
- Obtain a urine sample for urinalysis (Section 9.7).

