### 8.1. Pharmacokinetic Variables

Plasma concentrations (total and unbound) of DS-3201a will be used to determine the following PK parameters using standard non-compartmental method. Plasma concentration-versus-time data will be summarized using summary statistics by dose/study day/time.

Cycle 1/Days 1 and 2 (Part 1 and Part 2):

- Cmax, Tmax, AUClast
- If appropriate: AUCinf, t1/2, CL/F, Vz/F

Cycle 1/Day 8 (Part 1 and Part 2):

- Cmax, Tmax, AUClast, Cmax and AUClast ratio (d8,d1)
- If appropriate: AUCtau, AUCinf, t1/2, CLss/F, Vss/F

Cycle 1/Days 2, 8, 15, and 22 and Cycle 2/Day 1 (Part 1 and Part 2):

- Ctrough

End-of-treatment (Part 1 and Part 2):

- Ctrough

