f: If the ECG at 8 hours post-dose is not possible, then ECG may be performed at 6 hours ( $\pm$  10 minutes) post-dose.

g: All unscheduled bone marrow assessments of disease burden performed on non-visit days must be reported as unscheduled visits and samples for flow cytometry and/or mass cytometry, cytogenetics, and other biomarkers should be obtained.

i: Perform a bone marrow assessment if Cycle 2/Day 1 bone marrow revealed aplasia.

j: Blood samples drawn pre-dose at Cycle 1/Days 1, 2, 8, 15, and 22, Cycle 2/Day 1, and EOT visit for exploratory biomarker analysis.

k: DS-3201b is administered per protocol at the clinical site at the indicated time. Subjects should avoid food for 2 hours before and 1 hour after drug administration.

l: Blood samples for DS-3201a PK measurements and protein binding will be collected pre-dose at the indicated visits (Cycle 1/Days 1, 2, 8, 15, and 22, and Cycle 2/Day 1), at the indicated time points on Cycle 1/Days 1 and 8, and at EOT. Subjects will be instructed not to take their dose until after sample has been collected on clinic days. Additional samples will be collected at the indicated time points. The window for sample collection will be  $\pm$  15% of the specified time. Based on the PK profile established from the initial subjects treated in the study, sample collection time points may be modified upon notification by the Sponsor. Blood samples should be collected within 15 minutes of ECG collection on days with time matched ECGs and blood sampling.

m: If moderate or strong CYP3A and/or P-gp inhibitors are co-administered with DS-3201b, blood samples for DS-3201a PK measurements and protein binding should be collected on the first day of moderate or strong CYP3A and/or P-gp inhibitor dosing at pre-dose, 4 hours, and 8 hours post-dose of DS-3201b; and within 28 days after last day of moderate or strong CYP3A and/or P-gp inhibitor dosing at pre-dose, 4 hours, and 8 hours post-dose of DS-3201b.

n: Blood for histamine measurement will be obtained at the indicated time points (pre-dose and at 1, 2, and 6 hours post-dose on Cycle 1/Day 1 and pre-dose on Cycle 1/Days, 2, 8, and 15).

o: A bone marrow re-biopsy may be performed within 30 days of the last dose of DS-3201b in subjects who have achieved an initial complete remission/partial remission to DS-3201b by revised IWG response criteria or NCCN response criteria but later developed progressive disease while on therapy.

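### The Day 8/Day 1 AUClast ratio compares 0–8 h with 0–24 h whenever the Day 2 pre-dose sample is quantifiable, and so understates accumulation

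*Combined protocol and SAP*

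**What the plan says.** The ratio appears in four places: the Synopsis PK parameters; the List of Abbreviations, which explains the AUClast ratio as "Comparison of AUClast values between Day 8 and Day 1"; Section 3.1.3, with "Cmax, Tmax, AUClast, and comparison of Cmax and AUClast values between Day 8 and Day 1 (Cmax and AUClast ratio) (d8,d1"); and Section 8.1, with "Cmax, Tmax, AUClast, Cmax and AUClast ratio (d8,d1"). AUClast itself is defined up to the last quantifiable time, with no fixed end point.

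Sections 3.1.3 and 8.1 list the first-dose AUClast under a joint heading for Cycle 1 Days 1 and 2. Day 1 is sampled pre-dose and at 0.5, 1, 2, 4, 6 and 8 h (Sections 6.3.1.1 and 6.3.2.2). The Day 2 visit adds, before that day's dose, "Obtain a blood sample for DS-3201a PK measurement" (Section 6.3.1.2; the same in Section 6.3.2.3).

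On Day 8, samples are taken pre-dose and "at the following time points: 0.5, 1, 2, 4, 6, and 8 hours post-dose" (Section 6.3.1.3; the same in Section 6.3.2.4). Footnote l of Tables 17.2 and 17.3 has the remaining samples "collected pre-dose at the indicated visits (Cycle 1/Days 1, 2, 8, 15, and 22, and Cycle 2/Day 1"), so the next scheduled PK sample after Day 8 is on Day 15.

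Section 11.5.1 plans descriptive summaries by dose level and study day. It sets no common interval for the ratio.

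**The concern.** The Day 1 and Day 8 areas need not cover the same stretch of time. With a quantifiable 24 h sample, the denominator spans about 24 h and the numerator at most 8 h. The result mixes accumulation with the share of daily exposure that falls in the first 8 h.

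Two things are at stake. First, a value well below 1 could be read as falling exposure on repeated dosing when exposure is stable or rising. The protocol's own animal data lead one to expect a true ratio near 1: "There was no consistent evidence of accumulation after repeated dosing" (Section 1.1.1.5.3). Second, whether the 24 h sample is quantifiable may differ between subjects and between dose levels, which Section 11.11.3 lists from 100 to 700 mg and possibly 1000 mg. Differences in the ratio could then reflect assay sensitivity and not pharmacology.

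PK after single and multiple doses is a secondary objective in both Parts (Sections 2.1.2.1 and 2.1.2.2), and this ratio is a named parameter serving it.

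**Working it through.** The plan gives no numerical value for the ratio, so there is no figure to reproduce. The check has a model-free step and a simulated size.

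**Direction.** Write A8(0–8) for the Day 8 area to 8 h, and so on.

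- Planned ratio, 24 h sample quantifiable: A8(0–8) / A1(0–24).
- Accumulation over the dosing interval: A8(0–24) / A1(0–24).
- Planned ÷ true = A8(0–8) / A8(0–24), which is always below 1.

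**Inputs from the protocol.** Once-daily dosing (Section 3.1.2). Day 1 sampling at 0, 0.5, 1, 2, 4, 6, 8 and 24 h; Day 8 at 0 to 8 h after the eighth dose. The animal half-life "was from 2.29 hours to 7.14 hours in rats and from 1.73 hours to 5.88 hours in dogs" (Section 1.1.1.5.3).

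**Assumptions.** The documents give no human half-life, absorption rate or assay limit. I used a one-compartment oral model with ka of 0.5, 1 and 2 per hour, half-lives of 1.73 to 48 h, and the linear-up/log-down trapezoid at nominal times. After one dose, per unit of dose over volume:

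C(t) = ka/(ka − k) × (exp(−kt) − exp(−ka·t)), with k = ln 2 / half-life.

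The Day 8 profile is the sum of C(t + 24j) for j = 0 to 7. The true value uses a fine grid over 0–24 h on both days.

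**One case in full: half-life 7.14 h, ka = 1.**

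- Day 1 area: 4.979 over 0–8 h and 9.114 over 0–24 h.
- Day 8 area: 5.643 over 0–8 h, and 10.224 over 0–24 h with the Day 8 pre-dose value used at 24 h.
- Planned: 5.643 / 9.114 = 0.62.
- Matched 0–8 h: 5.643 / 4.979 = 1.13.
- AUCtau / AUC0-24h: 10.224 / 9.114 = 1.12.
- True: 1.12.

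**Ranges over ka 0.5 to 2, 24 h sample quantifiable:**

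| Half-life (h) | Planned ratio | True ratio |
|---|---|---|
| 2 | 0.84–0.92 | 1.00 |
| 4 | 0.66–0.75 | 1.02 |
| 7.14 | 0.58–0.64 | 1.11–1.14 |
| 12 | 0.60–0.64 | 1.35–1.39 |
| 48 | 1.20–1.22 | 3.26–3.44 |

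The planned ratio crosses 1 only at a half-life of 34.5 to 34.9 h. The linear trapezoid lowers it further (0.53–0.59 at 7.14 h).

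**When the mismatch disappears.** At 1.73 h the 24 h level is 0.01–0.07% of Cmax and may well be below the assay limit; both areas can then end at 8 h. At 4 h it is about 2–4% of Cmax, and at 7.14 h about 12–18%.

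**Mixed scales, half-life 4 h.** Subjects with a quantifiable 24 h value give 0.66–0.75; those without give 1.02–1.03. As an illustration, an even split has a geometric mean from √(0.66 × 1.03) ≈ 0.83 to √(0.75 × 1.02) ≈ 0.87, although true accumulation is 1.02 in everyone.

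**The case against.** The strongest counter-argument is about reading. The ratio is worded as Day 8 against Day 1, not against Days 1 and 2, and the Day 2 pre-dose sample is also listed as a trough. If the Day 1 area were confined to the Day 1 samples, both areas would end at 8 h. No section says which samples enter the ratio. However, the only first-dose AUClast in the plan sits under the joint Days 1 and 2 heading, and AUClast by definition uses the last quantifiable sample of the profile. The restricted reading is possible but the text disfavours it.

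Section 11.2 leaves detailed methods to a SAP to be finalized before database lock, and footnote l lets the Sponsor change sampling times. Either route could cure the problem, but neither sets an interval now. AUCtau is already listed for Day 8 where appropriate, so a matched comparison can be built from planned data. That makes the repair easy, but AUCtau is not the quantity the ratio names.

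Two points stand. The sizes depend on assumed kinetics: half-lives above the animal range have no support in the documents, and the evenly split cohort is only an illustration. The consequence is also limited. PK summaries are descriptive, the dose recommendation rests on the DLT model with PK as one further input, and the Cmax ratio and the troughs provide a cross-check that is free of the mismatch.

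**Conclusion.** The concern holds. As written, the AUClast ratio understates accumulation over the dosing interval in every subject whose 24 h sample is quantifiable and enters the first-dose AUClast. The direction needs no pharmacokinetic model. Under the stated one-compartment assumptions, the planned ratio at the top of the animal half-life range is little more than half the true value, and at 4 h about two-thirds to three-quarters of it. How many subjects are affected cannot be determined, because the documents give neither a human half-life nor an assay limit. The error is confined to a descriptive secondary PK parameter; no effect on dose decisions or on a primary endpoint is shown. It should be corrected before database lock.

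**What to change.** In the Synopsis, the List of Abbreviations, Section 3.1.3 and Section 8.1, replace the AUClast ratio with one ratio over a common interval, and keep AUClast as a per-day parameter only. Either of these works with the samples already planned:

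- **Day 8 AUCtau / Day 1 AUC0-24h**, with the Day 8 pre-dose concentration stated to serve as the Day 8 24 h value. In the model this is within 0.01 of the true ratio for half-lives up to 36 h and within about 0.02 at 48 h. It assumes steady state by Day 8 and needs quantifiable trough samples.
- **AUC0-8h on both days.** This needs no trough at 24 h, but covers only part of the dosing interval and overstates accumulation at long half-lives (1.37–1.49 against 1.35–1.39 at 12 h; 3.38–4.01 against 3.26–3.44 at 48 h).

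Use the chosen definition for all subjects and dose levels. The cost is a wording change in four places.
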